This stage is designed to determine if daily oral ACZ is tolerated and if tachyphylaxis might occur with long-term use for the specific formulation of oral ACZ that we will utilize. Some authors have reported attenuation of the initial increases in CBF with sustained use or oral ACZ though still showing a persistent increase in cerebral perfusion of between 15% - 20%, when compared to pre-treatment levels (Friberg et al., 1990). In this stage, all subjects will receive baseline pCASL and DSC MRI and will start oral ACZ. Patients will continue on 1000 mg BID dose for 24 consecutive weeks and undergo repeat imaging at predetermined intervals. MRI scans and clinical evaluations will be obtained every 6 weeks with contrast-based scans repeated every 12 weeks. Contrast will be administered every 12 weeks to determine DSC measures of blood flow and whether new lesions have formed. As previously stated, DSC provides measurements of not only CBF but also blood volume (CBV) and transit time of blood (MTT). DSC techniques will provide information that cannot be obtained by using pCASL alone that might be important to determine how blood flow is altered with ACZ.

Stage 3 - Many factors contribute to the formation and evolution of lesions in MS (Cotton et al., 2003; Meier and Guttmann, 2006; Narayana et al., 1998). As much as 60% of MS lesions resolve over six

months while the remainder show evidence of persistent damage (Sahraian et al., 2010). In this stage, all subjects will receive baseline pCASL and DSC MRI and will then be randomized to first receive either daily oral therapy with either "**Treatment A**", extended-release ACZ capsules or "**Treatment B**", placebo capsules for 24 consecutive weeks and undergo repeat imaging at predetermined intervals. MRI scans and clinical evaluations will be obtained every 6 weeks with contrast-based scans repeated every 12 weeks. Contrast will be administered every 12 weeks to determine DSC measures of blood flow and whether new lesions have formed and determine how blood flow is altered with ACZ.

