The primary aim of the proposed study is to evaluate the change in global CBF with ACZ, so the primary outcome is the change in global CBF after 24 weeks relative to pre-treatment baseline. Based on the preliminary data, we expect to see a 15% difference between the ACZ treatment and placebo groups on the improvement in global cerebral perfusion with standard deviation (SD) of 30%. We ran Monte Carlo simulations under a linear mixed effect model (same model as planned for analysis) and calculated a needed total sample size of n=50 to detect a group difference of 0.5 SD at the 24 weeks (phase 1) assuming a within-subject correlation of 0.5, a significance level of 0.05, and 90% power. We hypothesize a similar group difference in phase 2 (ACZ-ACZ group would not change between weeks 24 and 48 but delayed-start group would improve) and similar power to detect this effect. With 50 patients, for Aim 1.2, we will have 80% power to detect an average correlation as low as 0.39 between CBF and MD or FA. Considering a dropout rate of 18%, we need to recruit 60 participants. Aims 2 are mainly exploratory and parameters derived from this study will be used to help design future larger scale confirmatory studies.

All analyses will be intent-to-treat. To summarize the data, descriptive statistics will be used. Demographics and baseline characteristics at randomization will be summarized for each treatment arm. Generalized linear mixed models will be used to analyze all outcomes and will include treatment group and time, group-by-time interaction, and disease duration (stratifying variable) as covariates, and a random intercept to account for within-patient correlation.

For the primary outcome, we will focus on comparing the treatment groups in phase 1. A linear mixed model will be used to compare the estimated change in global CBF between baseline and week 24 in the ACZ and delayed-start groups. A secondary analysis will study ACZ treatment effect on CBF in different regions by treating regions as clusters in the linear mixed model. If normality of CBF outcome does not hold, an appropriate transformation or different outcome distribution will be used.

For the secondary endpoint at 48 weeks (phase 2), a similar mixed model will be used to compare changes in global CBF between weeks 24 and 48 weeks in the early-start and delayed-start groups. The model will include the same terms as for phase 1.

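### A random intercept alone imposes one correlation on every pair of scans; if all phase 1 scans are fitted and correlation fades with time, the week-24 standard error is too small

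*Combined protocol and SAP*

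**What the plan says.** Section 11 (Sample Size and Statistical Methods) gives one model form for all outcomes. Its fixed effects "will include treatment group and time, group-by-time interaction, and disease duration (stratifying variable) as covariates", and the only allowance for repeated measurement is "a random intercept to account for within-patient correlation". On the primary outcome, the section says "For the primary outcome, we will focus on comparing the treatment groups in phase 1" and "A linear mixed model will be used to compare the estimated change in global CBF between baseline and week 24" in the two groups. The sample size simulation used the same model, "assuming a within-subject correlation of 0.5, a significance level of 0.05, and 90% power".

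For Stage 3 the background text says "MRI scans and clinical evaluations will be obtained every 6 weeks with contrast-based scans repeated every 12 weeks", and the Stage 3 visit table marks pCASL at weeks 0, 6, 12, 18 and 24, then on to week 48 on treatment and week 50 off treatment.

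The plan states no random slope, residual correlation structure, robust standard error, degrees-of-freedom method or check of the equal-correlation assumption. Its one fallback concerns non-normal CBF. It does not list which scans enter the primary model, or say whether time is categorical or linear.

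**The concern.** A random intercept with independent residuals implies that scans 24 weeks apart are as strongly correlated as scans 6 weeks apart. The model takes its error for the week-24 change from the average over all visit pairs, but the true variance of that change depends only on the correlation between weeks 0 and 24. Within phase 1 no pair is further apart. If correlation fades with time, the average correlation exceeds the one that matters. The standard error is then too small, the interval too narrow and the p-value too low.

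The protocol gives some reason to doubt constant correlation. Its design rationale expects responders and non-responders, which implies patient-specific courses that an intercept alone cannot represent. The sample size simulation is no safeguard, because it was run under the same model with a single correlation. At stake are the primary p-value and interval of the only blinded, randomized stage.

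**Working it through.** **Inputs.** From section 11: 50 evaluable patients, correlation 0.5, alpha 0.05, contrast baseline to week 24. From the Stage 3 table: five phase 1 scans, hence 10 visit pairs. Assumed: 25 per arm, two-sided test, equal variance at each visit, complete data, categorical time, and the fading patterns themselves.

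**The plan's own case.** With every correlation at 0.5 the model is correct and the 5% level is reproduced (simulated 4.9% to 5.3% in separate runs). The stated 90% power is a separate matter. For a 0.5 SD difference in the week-24 change, the standard error is √(2 × (1 − 0.5) × 2/25) = 0.283 SD, which gives about 42% power at 25 per arm.

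**Formula.** With complete data and categorical time, the estimated effect equals the difference in mean change whichever of the two covariances is used. Per patient:

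- variance used by the model: 2σ²(1 − r̄), where r̄ is the mean of the pairwise correlations;
- true variance: 2σ²(1 − r₀₋₂₄);
- ratio V = (1 − r₀₋₂₄)/(1 − r̄);
- type I error ≈ 2[1 − Φ(1.96/√V)].

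Five visits give 4, 3, 2 and 1 pairs at gaps of 6, 12, 18 and 24 weeks.

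- Mild (0.55, 0.513, 0.477, 0.44): r̄ = 0.513; V = 0.56/0.487 = 1.15.
- Moderate (0.62, 0.54, 0.46, 0.38): r̄ = 0.54; V = 0.62/0.46 = 1.35.
- First-order decay, adjacent correlation 0.684: r₀₋₂₄ = 0.219; r̄ = 0.50; V = 0.781/0.50 = 1.56.

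| Pattern | Type I error, formula | Simulated, random intercept | Simulated, change tested with its own variance |
|---|---|---|---|
| Constant 0.5 | 5.0% | 5.3% | 5.3% |
| Mild | 6.8% | 6.7% | 5.1% |
| Moderate | 9.1% | 9.1% | 4.9% |
| First-order, mean 0.5 | 11.7% | 11.7% | 4.9% |

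The simulated columns use 20,000 null trials per pattern. Their simulation error near 5% is about √(0.05 × 0.95/20,000) = 0.15 percentage points.

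**Other readings of the plan.**

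- *Weeks 0 and 24 only.* There is one pair, so r̄ = r₀₋₂₄, V = 1 and type I error is 5%.
- *All nine scans from week 0 to week 48.* There are 36 pairs, and weeks 0 and 24 are no longer the extreme pair. Holding the mild and moderate correlations at their 24-week value for longer gaps, r̄ is 0.485, 0.478 and 0.357 for the three patterns. V is then 0.56/0.515 = 1.09, 0.62/0.522 = 1.19 and 0.781/0.643 = 1.21, giving 6.0%, 7.2% and 7.5%.
- *Change from baseline at four visits as the response.* Simulated type I error is 7.1% to 10.2% for first-order decay with adjacent correlation 0.5 to 0.841.
- *Linear time, five scans.* The problem is larger: 17.1% for first-order decay with mean correlation 0.5.

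**Other correlation shapes, five visits, categorical time.** A stable patient level plus partial decay plus scan noise gives 5.6% to 6.3%. First-order decay with adjacent correlation 0.3 to 0.9 gives 7.0% to 15.0%.

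**The case against.** The strongest reply is that the plan does not commit to a five-visit fit. It defines the primary outcome as a single change, and its sample size uses a single correlation. If only weeks 0 and 24 enter, nothing is wrong; if all scans to week 48 enter, the effect is modest. This stands as a limit on the conclusion. It does not remove the point: six-weekly scans and a group-by-time term make a multi-visit model the more natural reading, and the sponsor can settle the matter in a sentence.

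The size is also assumed. Pure first-order decay is towards the severe end, and a mix of stable patient level and scan noise gives little inflation. That stands too. The direction, given fading and a five-visit fit, is algebra.

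A third reply is that a random intercept is a legitimate prespecified choice in a pilot. True, but here it is applied to the contrast most exposed to its one restriction, and the alternative is cheap.

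Finally, the statement that only the standard error changes needs complete data. With the planned 18% dropout, the estimate may also differ slightly between the two models.

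A reader might infer that the trial's type I error does exceed 5%, or that every other outcome using these model terms is inflated to the same degree. The documents support neither. They give no correlation pattern and no list of fitted visits, and the effect depends on which visits a contrast compares and which are fitted.

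**Conclusion.** The concern holds conditionally. As specified, the random-intercept model protects the primary test only if correlation is the same at all gaps or only weeks 0 and 24 are fitted. If the five phase 1 scans are fitted and correlation fades, the standard error is too small. Illustrative type I error at 25 per arm is then about 6-7% (mild), 9% (moderate) and 12% (first-order, mean 0.5). With nine scans to week 48 it is about 6-7.5%. These figures assume 1:1 allocation, a two-sided test, equal visit variances, complete data, categorical time and decay patterns that the documents do not supply. The change should be made because the method is stated, it bears on the primary p-value and interval, and the replacement costs little.

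**What to change.** State in section 11 that the primary global CBF model uses the scans at weeks 0, 6, 12, 18 and 24, with visit as a category, an unstructured within-patient covariance and Kenward-Roger degrees of freedom. Prespecify the order of fallback if it does not converge: heterogeneous Toeplitz, then random intercept with robust standard errors that carry a small-sample correction, which matters at about 25 per arm.

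The cost is SAP wording. Five visits need 15 covariance parameters, from 50 to 60 patients. If correlation is truly constant and data are complete, the critical value rises from 1.972 to 2.011, and 2.011/1.972 = 1.02, so the interval is about 2% wider. The cost under 18% dropout was not calculated.

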There are regional differences in cerebral perfusion within the normal human brain. Cerebral perfusion is altered in many disease states, including MS. Altered perfusion has been seen in patients with all MS phenotypes and early in relapsing-remitting disease (Helenius et al., 2003; Papadaki et al., 2013, 2012; Wuerfel et al., 2004). Changes in cerebral perfusion both in a given region and lesion area have been previously described in multiple sclerosis (Juurlink, 2013; Wuerfel et al., 2004). Our own work is consistent with others showing that areas within the brain that are most prone to hypoperfusion appear to be those with minimal collateral flow (Adhya et al., 2006; Helenius et al., 2003; Holland et al., 2012; Juurlink, 2013; Narayana et al., 2014; Wuerfel et al., 2004). It is noteworthy that studies, including our own, have shown increased probability of lesion formation within areas corresponding to expected hypoperfused regions (Debernard et al., 2013; Holland et al., 2014). Diminished regional perfusion and increased energy demand has also been suggested to potentiate axonal loss within lesions and contributes to the evolution of potentially irreversible and progressive tissue injury, visualized on serial MRI as persistent black holes (Trapp and Stys, 2009). Indeed, these changes appear to be dynamic and

Protocol Number: HSC-MS-14-0450, Version No 6, April 1, 2019 Page 5

IRB NUMBER: HSC-MS-14-0450 IRB APPROVAL DATE: 06/27/2019 associated with lesion evolution (Wuerfel et al., 2004).

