At the end of week 24, patients initially randomized to Treatment B will take 1000 mg extendedrelease ACZ capsules. Similar imaging and clinical evaluations will be performed for the second 24week period. All subjects will discontinue drug at week 48 and obtain a follow-up clinical visit two weeks later. Based upon established pharmacokinetics, the half-life of drug is between 60-75 hours and one would expect insignificant levels within two weeks of discontinuation.

To maintain blinding, patients, evaluating clinicians and MRI analysts will not be informed of treatment assignment or sequence of scans.

We anticipate that sustained increases in regional cerebral perfusion over 6 months will result in improved tissue integrity as measured using diffusion tensor metrics and fewer MS lesions that evolve to persistent black holes.

HYPOTHESIS AND OBJECTIVES

Hypothesis

The underlying hypothesis of this proposal is that long-term therapy with ACZ will improve cerebral perfusion in subjects with MS and this improved perfusion will result in improved tissue integrity in a proportion of MS lesions. To test this hypothesis, subjects will be treated with ACZ, a currently FDA approved agent previously shown in healthy controls to increase cerebral perfusion (Sullivan et al., 1987; Vagal et al., 2009). Subjects will be scanned at various time points (see sections 4 and 6.3) and quantitative MRI metrics will be used to evaluate lesion evolution during and after discontinuation

of treatment.

Primary & Key Secondary Objective

Determine the degree to which divided daily doses of ACZ improves global and regional cerebral perfusion in subjects with MS.

Study subjects will obtain serial MRI scans prior to, during and after therapy (see sections 4 and 6.3). Cerebral blood flow will be measured using an optimized pCASL technique as described by Aslan (Aslan et al., 2010). This will allow us to test the first component of our hypothesis that treatment with ACZ will result in increased regional and/or global perfusion.

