Secondary outcomes considers repeated measures of MD or FA at different time in different regions. Linear mixed models will be used to evaluate changes in MD and FA from baseline (24 weeks for delayed-start) to 24 weeks (48 weeks for delayed-start) after ACZ therapy. These changes will be compared between regions with and without increased CBF (>15% difference from baseline). Terms in the model will be as for CBF with the addition of increased CBF (yes/no) for the region. Mixed models will also be used to compare MD and FA changes between white matter areas with and without lesions.

Logistic or linear mixed models will be used to evaluate change from baseline to after 24 week ACZ therapy (using phase 1 and phase 2 data) in the tertiary composite change outcome. Models will include the same terms as for analyses of the primary outcome. We will evaluate associations between changes in clinical outcomes and changes in CBF, CBV, and MTT by including each of these variables (one at a time) as a time-varying covariate.

As this trial uses a small sample size, we would not expect statistically significant treatment effects on clinical disability though this exploratory measure should be useful in power calculation for the anticipated larger, randomized clinical trial.

ETHICAL CONSIDERATIONS

Informed Consent

The informed consent form is a method of providing information regarding the trial to a prospective participant and allows for an informed decision about participation in the study. All participants (or their legally acceptable representative) must read, sign, and date a consent form before participating in the study, taking study drug, and/or undergoing any study-specific procedures. If a participant does not speak and read English, the consent materials will be translated into the Spanish.

The informed consent form will be updated or revised whenever important new safety information is available, whenever the protocol is amended, and/or whenever any new information becomes available that may affect a subject's participation in the trial.

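### As listed, the Stage 3 regional CBF model estimates one ACZ effect averaged over regions and names no region-specific ACZ-minus-placebo contrast

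*Combined protocol and SAP*

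**What the plan says.** The section Sample Size and Statistical Methods sets the model for every outcome: "Generalized linear mixed models will be used to analyze all outcomes and will include treatment group and time, group-by-time interaction, and disease duration", with "a random intercept to account for within-patient correlation". The regional CBF analysis then has one sentence: "A secondary analysis will study ACZ treatment effect on CBF in different regions by treating regions as clusters in the linear mixed model". It names no region factor, no region-by-treatment term, no treatment or time slope by region, and no region-specific contrast. The regions are neither listed nor counted, and no multiplicity rule for them is given.

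The paragraph on MD and FA in the same section does add a region-level term: "Terms in the model will be as for CBF with the addition of increased CBF (yes/no) for the region". So the CBF model is the base, and the one region-level covariate is added only for MD and FA.

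The analysis serves the first objective (Primary & Key Secondary Objective): "Determine the degree to which divided daily doses of ACZ improves global and regional cerebral perfusion in subjects with MS". The General Introduction explains the interest in regions: "areas within the brain that are most prone to hypoperfusion appear to be those with minimal collateral flow".

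**The concern.** The stated purpose is the ACZ effect in different regions, but the listed terms do not produce region-specific effects. A random intercept for a region shifts the level of CBF in that region. It does not let the ACZ-minus-placebo change differ between regions. One group-by-time coefficient remains, and it describes the average region.

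Three things follow. A rise limited to a few regions is diluted by the others. A moderate rise everywhere looks the same as a large rise in a few places. And the result comes close to repeating the primary global CBF analysis, so it adds little on where perfusion changed, which is what the regional rationale asks.

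**Working it through.** **1. Is there a plan figure to reproduce?** No. The plan gives no sample size, SD or power for the regional analysis. Its figures (a 15% difference, SD 30%, 50 patients in total) are for improvement in global CBF.

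**2. What the listed terms estimate.** For patient *i*, region *r* and visit *t*, the listed model is

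Y(irt) = intercept + group + time + θ(t)·group + disease duration + b(i) + c(ir) + error,

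where b and c are random intercepts for patient and region. θ carries no index *r*. If the true week-24 effects are d(1)…d(R) and the data are balanced, the estimate of θ has expectation Σd(r)/R.

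This was checked by simulation with 25 per arm, baseline and week 24, 4 regions, total SD 30, variance split 50% patient, 25% region within patient and 25% residual, and 40 runs per pattern. The number of regions and the variance split are assumptions.

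| True regional effects | Mean | Listed model | With region interactions |
|---|---|---|---|
| 15/15/15/15 | 15 | 15.0 | 14.2/15.1/15.5/15.2 |
| 60/0/0/0 | 15 | 14.7 | 60.0/-1.3/0.9/-0.7 |
| 30/30/0/0 | 15 | 14.4 | 28.9/30.9/-1.4/-0.9 |
| 15/15/-15/-15 | 0 | 0.1 | 14.5/17.1/-15.6/-15.6 |

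The listed model gives nearly the same answer to the first three patterns and sees nothing in the fourth. The three-way test rejected in 5% of runs under the uniform pattern and in all runs of the other three. With 40 runs and an assumed variance split, those rates are rough.

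**3. Size under a less extreme pattern.**

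- From the plan: "we expect to see a 15% difference between the ACZ treatment and placebo groups"; SD 30; 50 patients, taken as 25 per arm (the allocation ratio is not stated).
- Assumed: 8 equally weighted regions; a 15-point rise in 2 and none in 6; a fraction *s* of the variance of regional change shared within a scan; two-sided 5% tests on the week-24 change.

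Because the plan's SD is global, the mean over 8 regions is set to SD 30:

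- Regional SD: σ = 30/√(s + (1−s)/8). At s = 0.5 this is 30/√0.5625 = 40.
- Pooled effect: 15 × 2/8 = 3.75. Its SE is 30 × √(2/25) = 8.49, so the ratio is 0.44, and power on 48 df is about 7%.
- Interaction: Σ(d(r) − 3.75)² = 2 × 11.25² + 6 × 3.75² = 337.5. The noncentrality is λ = (25/2) × 337.5/[σ²(1−s)], on 7 and 7 × 48 = 336 df. At s = 0.5, λ = 12.5 × 337.5/800 = 5.27, and power is 33%.
- Half-width of one region's 95% CI: 2.011 × σ × √(2/25). At σ = 40 this is about 23.

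| Shared fraction s | σ per region | Pooled power | Interaction power | Regional half-width |
|---|---|---|---|---|
| 0.1 | 65.1 | 7% | 9% | 37 |
| 0.3 | 48.2 | 7% | 17% | 27 |
| 0.5 | 40.0 | 7% | 33% | 23 |
| 0.7 | 34.9 | 7% | 68% | 20 |

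**4. Sensitivity to the SD.** If 30 is assumed for each region instead, interaction power is about 41%, 57% and 83% at s = 0.3, 0.5 and 0.7, pooled power is 8–11%, and the half-width is 2.011 × 30 × √(2/25) = 17.1. But the mean over 8 regions would then have SD 30 × √(s + (1−s)/8) = 18.7, 22.5 or 25.8, below the 30 that the plan gives for global CBF.

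**The case against.** The strongest reply is that the plan is brief here rather than wrong. It gives one sentence and no equation, the common-effect structure is inferred from the term list, and treating regions as clusters could be stretched to include a treatment slope by region, which would give shrunken regional effects. That possibility stands, but the only random effect named is an intercept. If slopes were meant, the text still has to say so.

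A reader might infer that the regional half of the first objective goes unanswered, or that the trial cannot show regional effects at all. The documents do not support that. Under Rationale for Study Design, Stage 1a is to describe differences between regions after IV ACZ, and Stage 1b the CBF change by region under oral dosing. Stage 3 collects regional CBF and promises a comparison of imaging measures between treatments (Summary of Study Design). MD and FA changes are compared between regions with and without a CBF rise above 15%. None of these supplies the missing estimate, though: Stage 1 has no placebo arm, the Stage 3 promise is unspecified, and the MD/FA grouping is defined after treatment.

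A reader might also infer that a regional effect would usually be missed as planned and usually found with the added term. Both depend on the assumed pattern. The documents say that some regions are prone to hypoperfusion, not that ACZ acts only there, and with little shared variance the interaction test would usually miss the effect too.

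Finally, this is a secondary analysis in a pilot. That limits the weight of the point but does not remove it.

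**Conclusion.** The point holds for the Stage 3 between-arm regional estimate. As listed, the model gives one ACZ effect averaged over regions and no randomised region-specific contrast, although its stated purpose is the effect in different regions. This rests on the listed terms and does not depend on any assumed number. The primary global CBF analysis is unaffected.

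The size is uncertain because the number of regions, the response pattern, the regional SD and the shared variance are all assumptions. In the illustration scaled to the plan's global SD, the interaction test gains over the pooled 7% by an amount that runs from negligible (9%) to large (68%). The case for change is that the analysis should match its question. High power for that question is not assured.

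**What to change.** Before unblinding, amend the regional CBF paragraph of the statistical section:

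- List the regions.
- Enter region as a fixed factor with region-by-group, region-by-time and region-by-group-by-time terms, keep the existing terms, and nest regions within patient in the random effects.
- Test the three-way term at week 24 as the regional question.
- Report each region's ACZ-minus-placebo change from baseline to week 24 with a 95% CI, adjusted for multiplicity (for example Holm) if single regions are to be singled out.
- Keep the average over regions as a summary.

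If only a pooled effect is wanted, the listed model can stay, but the stated purpose of the analysis and the regional part of the objective should be reworded to match.

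The cost is SAP wording and a few model terms, with no new scans, patients or data. The downside is wide regional intervals and possibly modest interaction power. The plan should state both, so that a non-significant interaction is not read as evidence of a uniform effect.

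### The regional CBF, MD and FA models name no scan-level random effect, so tests averaged over regions can have a type I error well above 5% when repeated raw values are modelled

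*Combined protocol and SAP*

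**What the plan says.** Everything relevant is in the combined protocol and SAP, section 11 (Sample Size and Statistical Methods).

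- All outcome models contain treatment group, time, group-by-time, disease duration and "a random intercept to account for within-patient correlation".
- The regional CBF analysis is a secondary analysis and differs from the global one only by "treating regions as clusters in the linear mixed model". The text does not say whether regions are crossed with patients or nested in them, how many there are, or whether treatment effects are averaged over regions or estimated one by one.
- For the diffusion measures, "Secondary outcomes considers repeated measures of MD or FA at different time in different regions". The models use the CBF terms plus a yes/no for whether the region's CBF rose by more than 15%. They assess change over 24 weeks of ACZ, compare regions with and without increased CBF, and compare white matter with and without lesions.

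No patient-by-visit effect, residual covariance structure, random slope or robust variance is named. The Stage 3 schedule has pCASL at weeks 0, 6, 12, 18 and 24 in the first period, so each patient contributes five scans, each with several regions.

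**The concern.** Whatever shifts a whole scan moves all regions of that patient-visit together. For pCASL this could be that day's global flow or the labelling efficiency. A patient intercept, a region intercept and a patient-by-region intercept are each constant over visits, so none of them can absorb such a shift. When the model estimates a change over time averaged over regions, it treats one scan-wide shift as a separate piece of evidence from each region, and the standard error can be too small.

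Regional CBF and the MD/FA changes are secondary results meant to inform a larger trial. If their intervals are too narrow, a regional effect that is partly scan noise could be carried forward as a finding.

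**Working it through.** **1. The plan's own figure for these outcomes.** The only stated figure is a detectable correlation of 0.39 between CBF and MD or FA with 50 patients and 80% power. By Fisher's z, n = ((1.960 + 0.842)/atanh(0.39))² + 3 = (2.802/0.4118)² + 3 = 49.3, so 50. The figure reproduces, and it counts patients, not regions. No power or error rate is given for the regional mixed models.

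**2. Inputs.** From section 11: 50 evaluable patients, five scans in the first period, significance level 0.05. Assumed: 25 per arm, two-sided testing, R regions (4 or 10), and f, the share of within-patient variance common to all regions of one scan (0.10, 0.25 or 0.50).

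**3. Formula.** Let w be the within-patient variance of one regional value at one visit, with f·w shared by the scan and (1−f)·w specific to the region. The mean over R regions of a scan then has variance w[f + (1−f)/R] = (w/R)[1 + (R−1)f]. A model without a scan term uses w/R. The variance of the pooled group-by-time contrast is therefore understated by the factor 1 + (R−1)f, and

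type I error = 2(1 − Φ(1.96/√(1 + (R−1)f))).

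| R | f | 1+(R−1)f | 1.96/√ | Type I error |
|---|---|---|---|---|
| 4 | 0.10 | 1.30 | 1.72 | 8.6% |
| 4 | 0.25 | 1.75 | 1.48 | 13.8% |
| 4 | 0.50 | 2.50 | 1.24 | 21.5% |
| 10 | 0.10 | 1.90 | 1.42 | 15.5% |
| 10 | 0.25 | 3.25 | 1.09 | 27.7% |
| 10 | 0.50 | 5.50 | 0.84 | 40.3% |

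**4. Simulation under no effect** (50 patients, five scans, patient-by-region intercepts fitted). The pooled week-24 test rejects in about 9%, 14% and 22% of runs with R = 4, and 15%, 28% and 41% with R = 10. With a scan-level effect added, it rejects in 4.3% to 5.5%. The MD/FA mean change over time without a scan term gives about 15%, 29% and 40–42% with R = 10.

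**5. Is f likely to be near zero?** Section 11 takes an SD of 30% for global CBF, "assuming a within-subject correlation of 0.5". The within-patient variance is then 0.5 × 30² = 450, an SD of about 21%; if 30% is the SD of the change, 30²/2 is also 450. Assume that global CBF is roughly the mean of R regions. With R = 10 and no shared component, the regional error variance would have to be 10 × 450 = 4500, an SD of 67%. With an assumed regional error SD of 30%, the shared variance is 450 − 900/10 = 360, so f = 360/(360 + 900) = 0.29 and the type I error is about 30%. With 40% it is 450 − 160 = 290, f = 0.15 and about 20%. With R = 4 the same two SDs give about 12% and 6%.

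**6. Readings with less or no inflation.**

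- Patient-only intercept, with patient-by-region variance equal to the within-patient variance: about 2–11% with R = 4 and about 6%, 15% and 26% with R = 10. The unmodelled regional variance inflates the residual and offsets the shared error.
- One week-24 change score per region with a patient intercept: about 5%, because the intercept then absorbs the shared error. Change scores at all four follow-up visits: 5–12%.
- Group-by-time tested region by region with a patient intercept: 5.2–6.3% per region, or about 1% with large patient-by-region variance.
- MD/FA in regions with versus without increased CBF (R = 10–20, f = 0.25–0.50, patient-by-region intercepts): about 5% if the yes/no status varies freely within patients, 13–35% if half of its variation is between patients, and 25–52% if nearly all is.
- A fixed contrast of half the regions against the other half: 0.9–3.9%, which is conservative because the shared error cancels.

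**The case against.** The strongest reply is that the plan is under-specified rather than shown to be wrong. R and f are not in the documents. The variance factor in step 3 assumes that patient-by-region variance is modelled or negligible. Section 11 uses the language of change from baseline, and a single change score per region is analysed correctly with a patient intercept. Treatment effects in different regions may mean one effect per region, where the shared error does little harm. Two of the stated MD/FA comparisons set regions against each other, so shared error largely cancels. The physical causes are also clearer for pCASL than for diffusion imaging.

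Most of this stands, and it limits the size of the problem. It does not remove it. Explicit time and group-by-time terms, and repeated measures of MD and FA over time and regions, fit a model of repeated raw values better than a single change score. On that reading no listed term captures scan-level error.

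A reader might infer that every regional, MD and FA test is far above 5% under any reading of the cluster wording, or that the trial would report scan noise as effects. The documents support neither. They do not fix R, f or the random-effects structure, and several admissible readings give about 5% or less.

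**Conclusion.** The point holds for effects averaged over regions: the regional CBF group-by-time test and the MD/FA mean change over time, when repeated raw values are modelled. With patient-by-region intercepts, the nominal 5% becomes roughly 9–22% with 4 regions and 15–41% with 10, for f between 0.10 and 0.50. These sizes rest on assumed R and f, 25 patients per arm and two-sided testing. The plan's own SD and correlation make a negligible f unlikely for CBF if global CBF approximates the mean of the regions. There is no comparable figure for MD and FA.

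Contrasts between regions of the same scan are inflated only as far as the yes/no status clusters by patient, and can otherwise be conservative. The primary 24-week and secondary 48-week analyses of global CBF use one value per scan and are not affected.

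**What to change.** In the regional CBF, MD and FA models, specify random effects for patient, patient-by-region and patient-by-visit. Alternatively, use patient-clustered robust standard errors with a small-sample correction, given about 25 patients per arm. State that the group-by-time effect averaged over regions is tested against patient-by-visit variation. In the same paragraph, give the number of regions, say whether the outcome is the raw value or the change from baseline, and say whether effects are averaged over regions or reported for each.

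The cost is SAP wording and one more variance component, with no new data. Intervals for effects averaged over regions become wider. Intervals for contrasts within a scan may become narrower.
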